15.4.1. Handling of missing age

If age is missing but year of birth is collected, then age will be derived as year of informed consent signed minus year of birth.

15.4.2. Handling of computation of study intervention duration if investigational medicinal product end of treatment date is missing

For the calculation of the study intervention duration, the date of the last dose of IMP is equal to the date of last administration reported on the eCRF “Treatment status” page. If this date is missing, the last available administration date in the “Exposure” form will be used.

The last dose intake should be clearly identified in the eCRF and should not be approximated by the last returned package date.

15.4.3. Handling of medication missing/partial dates

No imputation of medication start/end dates or times will be performed. If a medication date or time is missing or partially missing and it cannot be determined whether it was taken prior or concomitantly, it will be considered a prior, concomitant and post-treatment medication.

15.4.4. Handling of adverse events with missing or partial date/time of onset

Missing or partial adverse event onset dates and times will be imputed so that if the partial adverse event onset date/time information does not indicate that the adverse event started prior to study intervention or after the study intervention period, the adverse event will be classified as treatment emergent. No imputation of adverse event end dates/times will be performed. These data imputations are for categorization purpose only and will not be used in listings. No imputation is planned for date/time of adverse event resolution.

15.4.5. Handling of adverse events when date and time of first investigational medicinal product administration is missing

When the date and time of the first IMP administration is missing, all adverse events that occurred on or after the day of randomization should be considered as treatment-emergent adverse events. The exposure duration should be kept as missing.

The last dose intake should be clearly identified in the eCRF and should not be approximated by the last returned package date.

15.4.6. Handling of missing assessment of relationship of adverse events to investigational medicinal product

If the assessment of the relationship to IMP is missing, then the relationship to IMP has to be assumed and the adverse event considered as such in the frequency tables of related adverse events, but no imputation should be done at the data level.

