5. PARTICIPANT DISPOSITION

5.1. Disposition

The participant disposition will be summarized for the ITT analysis set by study intervention group and overall using number and percentage. This section describes participant disposition for both participant study status and the participant analysis sets.

For participant study status, the number and percentage of participants in the following categories will be presented:

- Screened participants
- Screen failure participants
- Participants treated without being randomized
- Randomized participants
- Randomized but not treated participants
- Randomized and treated participants
- Participants who have completed the study intervention period
- Participants who discontinued the study intervention period and the main reason for study intervention discontinuation. Relationship with COVID-19 will be reported for “Adverse Event” and “Other” reasons.
- Participants who completed the study
- Participants who discontinued the study and the main reason for study discontinuation. Relationship with COVID-19 will be reported for “Other” reasons
- Participants who discontinued the study before Week 24
- Participants who discontinued the study after Week 24 (ie, during post-study intervention follow-up period)
- Participants who had rescue medications during the study intervention period:
 - Participants who have completed the study intervention period and had rescue medications
 - Participants who did not complete the study intervention period and had rescue medications
- Final Study Status

For screened, screen failure, and participants treated without being randomized, percentages will be calculated using the number of screened participants as the denominator for overall only.

All other categories of participants will be presented by randomized study intervention group and for overall whilst the percentages will be calculated using the number of randomized participants, within each study intervention group and overall, as denominator. Reasons for study intervention and study discontinuation will be supplied in the disposition table showing number and percentage by study intervention group.

A summary of all the analysis sets for safety and efficacy (ITT) will be summarized for the ITT analysis set by study intervention group and overall using number and percentage.

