9. SAFETY ANALYSIS

All safety results will be summarized using the safety set by actual study intervention group.

The observation periods include:

- The **pre-treatment** period is defined as the time from the signed informed consent date up to first administration of the IMP.
- The **treatment-emergent adverse event (TEAE)** period is defined as the time from the first administration of the IMP (on Day 1) to the last administration of the IMP +98 days and up to the end of the study follow-up.
- The **post-treatment** period is defined as the time starting 1 day after the end of the TEAE period up to the end of the study follow-up.

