9.1. Adverse events

The adverse event types include:

- **Pre-treatment adverse events** are adverse events that developed or worsened or became serious during the pre-treatment period.
- **Treatment-emergent adverse events** are adverse events that developed or worsened or became serious during the TEAE period.
- **Post-treatment adverse events** are adverse events that developed or worsened or became serious during the post-treatment period. AEs categorized as post-treatment AEs (following the rules specified below) will not be summarized.

The primary focus of adverse event reporting will be on TEAEs. Pre-treatment adverse events will be summarized separately.

All AEs will be coded by LLT, PT, HLT, HLGT, and associated primary SOC using the version of Medical Dictionary for Regulatory Activities (MedDRA) currently in effect at Sanofi at the time of each database lock.

Adverse events will be recorded from the time of signed informed consent until the end of the study or the resolution/stabilization of all SAE and AESI.

If an adverse event date/time of onset (occurrence, worsening, or becoming serious) is incomplete, an imputation algorithm will be used to classify the adverse event as pre-treatment, treatment-emergent, or post-treatment. The algorithm for imputing date/time of onset will be conservative and will classify an adverse event as treatment-emergent unless there is definitive information to determine it is pre-treatment or post-treatment. Details on classification of adverse events with missing or partial onset dates are provided in [Section 15.4.5](#).

Adverse events will be summarized by primary SOC, HLGT, HLT, and PT, sorted by internationally agreed order of primary SOC and then alphabetically for the other levels, for each study intervention group using number and percentage of participants experiencing an adverse event. Multiple occurrences of the same event in the same participant will be counted only once in

the tables within an observation period (pre-treatment period or TEAE period). The denominator for computation of percentages will be the safety analysis set within each study intervention group. Participants experiencing asthma exacerbations will be further summarized using the LLT level as appropriate within adverse event summaries.

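### The SAP's default for partially dated adverse events stops at the end of dosing, while its treatment-emergent period runs to last dose + 98 days: the two end points conflict and should be aligned

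*SAP*

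**What the plan says.** SAP 15.4.4 covers adverse events (AEs) with a missing or partial onset date. Where the available information does not indicate that the event "started prior to study intervention or after the study intervention period, the adverse event will be classified as treatment emergent". The imputation serves only to categorise the event.

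SAP Section 9 defines the TEAE period as running from the first administration of study drug "to the last administration of the IMP +98 days and up to the end of the study follow-up". The post-treatment period is the "time starting 1 day after the end of the TEAE period up to the end of the study follow-up".

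SAP 9.1 calls the algorithm for incomplete onset dates conservative: it "will classify an adverse event as treatment-emergent unless there is definitive information to determine it is pre-treatment or post-treatment". It continues: "Details on classification of adverse events with missing or partial onset dates are provided in" Section 15.4.5. That section deals with a missing date of first dose; the onset-date rule is in 15.4.4. On reporting, 9.1 states: "AEs categorized as post-treatment AEs (following the rules specified below) will not be summarized".

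Study intervention period has no formal definition. SAP 5.1 has a disposition line for "Participants who discontinued the study after Week 24 (ie, during post-study intervention follow-up period", and SAP 7.2.2 measures compliance over the administrations planned in the study intervention period. Both uses point to the dosing period.

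Protocol 9.4.2 ends the treatment-emergent period at last dose + 12 weeks, or on the day before a switch to commercial dupilumab or another biologic if that is earlier.

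**The concern.** The appendix rule and the main text use different upper bounds. Section 9 makes an event in follow-up treatment-emergent up to 98 days after the last dose. Section 15.4.4 withdraws the default as soon as a partial date shows onset after dosing. Two events on the same day could then be classified differently because one record lacks the day of the month.

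The main text does not settle this for a programmer, because 9.1 sends the reader to 15.4.5, which says nothing about partial onset dates. The rule that does apply is the one with the mismatched bound.

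At stake is the incidence of TEAEs, a secondary safety endpoint, in a trial of about 97 participants where one or two events can change a table row. Any misclassification from this wording would run one way, towards too few TEAEs. It would affect follow-up, which has a single scheduled contact, the Visit 6 telephone call.

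**Working it through.** The plan states no figure here to reproduce. The check compares the rules on one example and then counts days.

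**Example.** Last dose on some day in January; onset recorded only as March of the same year, during follow-up.

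- Section 9: the earliest possible last dose is 1 January. Adding 98 days gives 9 April (8 April in a leap year). Every day in March lies inside the TEAE period.
- Section 9.1: nothing shows definitively that the event is post-treatment, so it is treatment-emergent.
- Section 15.4.4 read literally: March is wholly after dosing, so the default does not apply. The section does not say what the event becomes.

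**Length of the affected stretch.** Inputs: Day 1 is the first dose; follow-up runs to Week 36 = day 1 + 36 × 7 = 253; the TEAE period ends at last dose + 98 days, capped by follow-up. The documents do not settle whether the last planned dose is at Week 22 or Week 24, so both are shown.

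- Last dose at Week 22: day 1 + 22 × 7 = 155. The TEAE period ends on day 155 + 98 = 253. Days after the last dose: 98. Share: 98/253 = 39%.
- Last dose at Week 24: day 1 + 24 × 7 = 169. Then 169 + 98 = 267, which is past Week 36, so the period is capped at day 253. Days after the last dose: 253 − 169 = 84. Share: 84/253 = 33%.

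In both cases the TEAE period covers all planned follow-up. For a participant who completes treatment, the post-treatment category should be empty or nearly so.

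**Which partial dates are affected.** The known month and year must place onset wholly after dosing. Counting every follow-up day over 365 possible start dates, with onsets spread evenly and only the day missing, the onset month lies wholly after dosing for 82.5% (84-day stretch) to 85% (98-day stretch). In the other 15% to 17.5% the month overlaps dosing and the event keeps its default under both texts. So does an event with no date at all.

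**Scale, on assumed rates only.** The documents give neither the follow-up AE rate nor the frequency of partial dates. Assume 0.3 to 0.6 follow-up AEs per participant, 5% to 10% of them partially dated with only the day missing, and 97 participants:

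- Low: 97 × 0.3 × 0.05 × 0.825 = 1.2 events.
- High: 97 × 0.6 × 0.10 × 0.85 = 4.9 events.

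These are the events exposed to the conflict if 15.4.4 is applied literally. If 9.1 governs, none is lost.

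**The case against.** A reader might infer that the SAP drops follow-up events from the safety tables whenever the onset day is missing. The documents do not support that, for four reasons.

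- Section 15.4.4 says if, not only if. It gives a sufficient condition for the default and does not say that other events become post-treatment.
- Sections 9 and 9.1 point the other way. The post-treatment period starts only after the + 98-day window, and 9.1 requires definitive information before an event leaves the treatment-emergent category. A careful programmer would impute a date and apply Section 9.
- A missing day is not enough, as the count above shows.
- Affected events do not vanish. SAP 9.1 plans individual listings of AEs, serious AEs and AEs of special interest, and SAP 9.1.9 tabulates deaths by period, including post-treatment. Serious events and those of special interest must be reported within 24 hours (protocol 8.3.1), so they are the least likely to lack a date.

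The meaning of study intervention period is also an inference from usage, and the rule applies alike to both arms.

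All of this stands, and it reduces the point from a stated loss to a risk created by conflicting rules. It does not remove the conflict. Where the SAP means the longer window it says so in days, in Section 9 and in 7.1.2 and 7.1.3, so reading 15.4.4 as the TEAE period is not natural. Protocol 9.4.2 does ask for a separate summary of serious AEs outside the treatment-emergent period, but SAP 9.1 plans no summary of post-treatment AEs, so the SAP does not carry that safeguard forward.

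**Conclusion.** The concern holds as a conflict of wording with a one-sided risk. The bound in 15.4.4 does not match the TEAE period in Section 9 or the conservative rule in 9.1, and the cross-reference in 9.1 is wrong. If 15.4.4 is programmed literally and the affected events are then classed as post-treatment, they leave the TEAE summaries and remain in the listings.

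The stretch concerned is about 33% to 39% of the planned TEAE period, for a treatment completer followed to Week 36 with a last dose at Week 24 or Week 22. That is a share of time, not of events. The number of events cannot be derived from the documents; the 1.2 to 4.9 above rests on assumed rates and is meant only to show that it is likely small. No efficacy result is affected.

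**What to change.** In SAP 15.4.4, replace *after the study intervention period* with *after the end of the TEAE period defined in Section 9*. In SAP 9.1, change the cross-reference from 15.4.5 to 15.4.4.

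Also reconcile the SAP window (last dose + 98 days, with no cut-off at a switch) with protocol 9.4.2 (last dose + 12 weeks = 84 days, or the day before a switch). The windows differ by 98 − 84 = 14 days, and the corrected rule needs one agreed window to refer to.

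The first two changes are one phrase and one section number, made before database lock. A few more events may be counted as treatment-emergent, which is what 9.1 already intends. Agreeing the window needs a decision by the sponsor, recorded in the SAP, but no new data.

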15.4.7. Handling of missing severity/grades of adverse events

If the severity/grade is missing for 1 of the treatment-emergent occurrences of an adverse event, the maximal severity on the remaining occurrences will be considered. If the severity is missing for all the occurrences, a “missing” category will be added in the summary table.

15.4.8. Handling of potentially clinically significant abnormalities

For PCSAs with 2 conditions, one based on a change from baseline value or a normal range and the other on a threshold value, with the first condition being missing, the PCSA will be based only on the second condition.

15.5. Visit windows

The analysis window below “[in brackets]” will be applied to post-baseline measurements to allocate them to a scheduled visit for the parameter (see [Appendix 15.2](#) for details of scheduled visits).

Table 15-2 Analyses window definition

Scheduled visit post-baseline	Targeted study day*	Visit window		
		AQLQ(S)	FRI and ACQ	Biomarkers, Forced Oscillometry, Spirometry and Vital signs
Week 4 (Visit 3)	29		[2, 98]	[2, 56]
Week 12 (Visit 4)	85			[57, 126]
Week 24 (Visit 5)	169	[2, ∞]	[99, ∞]	[127, ∞]

* The reference day (denoted as Day 1) for the calculation of study day will be the day of the first administration of IMP (except for participants randomized but not exposed). (See [Section 4.4.6](#)).

After applying the above time windows, if multiple assessments are associated to the same time point, the closest from the targeted study day will be used. In case of equality, the last measurement will be used. Re-allocated scheduled visits (ie, visit numbers) should be sequential if ordered by the date of measurement.

If there is no measurement available for a given parameter in an analysis window, data is considered missing for the corresponding visit.

15.6. Search criteria for AESI

Table 15-3 Search criteria for AESI

AESI	Search Criteria
Anaphylactic reactions	Anaphylactic reactions: includes anaphylactic reaction narrow SMQ (20000021) terms and programmatic identification of cases based on occurrence of at least two preferred terms meeting the algorithm criteria occurring within 2 consecutive days of each other
Systemic hypersensitivity reactions	SMQ: Hypersensitivity [Narrow]
Helminthic infections	HTLs of “Helminthic infections NEC”
Keratitis	PTs of 
 • Keratitis, Allergic keratitis • Corneal infection • Ulcerative keratitis • Atopic keratoconjunctivitis • Herpes ophthalmic • Ophthalmic herpes simplex
Any severe type of conjunctivitis or blepharitis	1. Conjunctivitis is defined as the following PTs with intensity “severe” in eCRF AE page: 
 • Adenoviral conjunctivitis • Conjunctival irritation • Conjunctival oedema • Conjunctival ulcer • Conjunctivitis • Conjunctivitis allergic • Conjunctivitis chlamydial

AESI	Search Criteria
	
• Conjunctivitis gonococcal neonatal• Conjunctivitis tuberculous• Conjunctivitis viral• Giant papillary conjunctivitis• Inclusion conjunctivitis• Ophthalmia neonatorum• Seasonal allergy• Herpes simplex virus conjunctivitis neonatal• Conjunctival hyperaemia• Inclusion conjunctivitis neonatal• Conjunctivitis bacterial• PingueculitisPhotoelectric conjunctivitis• Oculorespiratory syndrome• Acute haemorrhagic conjunctivitis• Blebitis• Ligneous conjunctivitisNoninfective conjunctivitis• Oculoglandular syndrome• Conjunctivitis fungal• Conjunctival suffusion• Giant fornix syndrome 
2. Blepharitis is defined as the following PTs with intensity “severe” in eCRF AE page:
 
• Abscess of eyelidBlepharitis• Blepharitis allergic• Blepharochalasis• Chalazion• Dacryoadenitis acquired• Dacryocanaliculitis• Dacryocystitis• Eczema eyelids• Erythema of eyelid• Eyelid boil• Eyelid infection• Eyelid oedema• Hordeolum• Lacrimal sac cellulitis• Meibomianitis• Swelling of eyelid• Swollen tear duct• Lid margin discharge• Meibomian gland discharge• Eyelid margin crusting• Bacterial dacryocystitis• Eyelid folliculitis• Eyelid irritation• Eyelid cyst• Meibomian gland dysfunction• Inflammation of lacrimal passage• Eyelid rash

AESI	Search Criteria
	
 • Staphylococcal blepharitis • Bacterial blepharitis • Lacrimal gland abscess • Demodex blepharitis
Clinically symptomatic eosinophilia (or eosinophilia associated with clinical symptoms)	CMQ10641 based on HLT=Eosinophilic disorders or PT=Eosinophil count increased followed by blinded medical review for selection of relative events
Significant ALT elevation	
 - ALT $>5 \times$ the ULN in participants with baseline ALT $\leq 2 \times$ ULN or - ALT $>8 \times$ ULN if baseline ALT $>2 \times$ ULN
Pregnancy of a female participant entered in a study as well as pregnancy occurring in a female partner of a male participant entered in a study with IMP	“Pregnancy” or “Partner Pregnancy” checked in eCRF form “Pregnancy”
Symptomatic overdose (serious or nonserious) with IMP/NIMP	“Overdose of Study Treatment” or “Overdose of NIMP” checked and “Symptomatic overdose” checked in eCRF form “Overdose”

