Based on the available sales figures and World Health Organization defined daily dose of 21.4 mg for parenteral formulations, the cumulative patient exposure in marketed experience is estimated to be 926 369 patient years from 01 March 2017 through 30 September 2022, including 220 161 patient years during the interval period from 01 April 2022 through 30 September 2022. The adverse drug reactions identified to date for dupilumab include injection site reactions, conjunctivitis (including allergic and bacterial), oral herpes, herpes simplex, blepharitis, dry eye, eye pruritus, keratitis, ulcerative keratitis, eosinophilia, enterobiasis and anaphylactic reaction, angioedema, serum sickness and arthralgia. These adverse drug reactions occur with relatively low frequency with dupilumab treatment, and were generally mild or moderate, transient, and manageable. More significant serious allergic reactions were very rare. Importantly, no increased overall infection risk was observed in patients treated with dupilumab.

Systemic hypersensitivity has been established as an important identified risk with dupilumab. As protein therapeutics, all monoclonal antibodies are potentially immunogenic. Rare serious and systemic hypersensitivity reactions have been observed in the dupilumab program including serum sickness/serum sickness-like reaction in the adult AD program and anaphylaxis related to dupilumab in the adult asthma clinical trials.

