3 OBJECTIVES AND ENDPOINTS

Table 1 - Objectives and endpoints

Objectives	Endpoints
Primary 
• To assess the effect of dupilumab on lung inflammation and related changes in airway volumes detectable by functional respiratory imaging.	
• Proportion of participants achieving FeNO <25 parts per billion (ppb) at Week 24• Percent change from baseline to Week 24 in untrimmed distal airway volumes corrected for lung volume ([s]iVaw) at total lung capacity (TLC)
Secondary 
• To evaluate the effect of dupilumab at Week 24 on bronchodynamics, hyperinflation, airway resistance, airway wall thickness, ventilation defects and mucus plugging derived from high-resolution computed tomography (HRCT) scans, patient-reported outcomes, FeNO and spirometry.• To evaluate safety of dupilumab	
Efficacy endpoints:
 
• Percent change from baseline to Week 24 in untrimmed distal airway volumes corrected for lung volume ([s]iVaw) at functional residual capacity (FRC)• Percent change from baseline to Week 24 in trimmed distal airway resistance corrected for lung volume ([s]iRaw) at TLC• Percent change from baseline to Week 24 in trimmed distal airway resistance corrected for lung volume ([s]iRaw) at FRC• Change from baseline to Week 24 in global lung lobar volumes (iVlobes) at TLC• Change from baseline to Week 24 in HRCT-based internal airflow distribution (IAD) for each lung zone• Change from baseline to Week 24 in image-based ventilation/perfusion (iV/Q) at TLC for each lung zone• Change from baseline to Week 24 in global lung mucus scoring (UCSF mucus scoring)• Change from baseline to Week 24 in FeNO• Change from baseline to Week 24 in pre-bronchodilator FEV₁• Change from baseline to Week 24 in post-bronchodilator FEV₁• Change from baseline to Week 24 in ACQ-7 
Safety:
 
• Incidence of treatment emergent adverse events (TEAE) and serious adverse events (SAE) including clinically significant changes in vital signs and laboratory abnormalities• Incidence of adverse events of special interest (AESI)

Objectives	Endpoints

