8.3 ADVERSE EVENTS AND SERIOUS ADVERSE EVENTS

Adverse event of special interest

An adverse event of special interest (AESI) is an AE (serious or nonserious) of scientific and medical concern specific to the Sponsor's product or program, for which ongoing monitoring and immediate notification by the Investigator to the Sponsor is required. Such events may require further investigation in order to characterize and understand them. Adverse events of special interest may be added, modified or removed during a study by protocol amendment.

For these AESIs, the Sponsor will be informed immediately (ie, within 24 hours), per SAE notification described in [Section 8.3.4](#), even if not fulfilling a seriousness criterion, using the screens in the e-CRF.

- Clinically symptomatic eosinophilia (or eosinophilia associated with clinical symptoms).
- Anaphylactic reactions.
- Systemic hypersensitivity reactions.
- Helminthic infections.
- Keratitis
- Any severe type of conjunctivitis or blepharitis
- Significant ALT elevation:
 - ALT $>5 \times$ ULN in participants with baseline ALT $\leq 2 \times$ ULN;
or
 - ALT $>8 \times$ ULN if baseline ALT $>2 \times$ ULN.
“Baseline” refers to ALT sampled at baseline visit or, if baseline value is unavailable, to the latest ALT value before the baseline visit
- Pregnancy of a female subject entered in a study as well as pregnancy occurring in a female partner of a male subject entered in a study with IMP;
 - Pregnancy occurring in a female participant entered in the clinical trial or in a female partner of a male participant entered in the clinical trial. It will be qualified as an SAE only if it fulfills one of the seriousness criteria,
 - In the event of pregnancy in a female participant, IMP should be discontinued,
 - Follow-up of the pregnancy in a female participant or in a female partner of a male participant is mandatory until the outcome has been determined.
 - Any pregnancy complication or elective termination of a pregnancy for medical reasons will be reported as an AE or SAE.
 - Abnormal pregnancy outcomes (eg, spontaneous abortion, fetal death, stillbirth, congenital anomalies, ectopic pregnancy) are considered SAEs.
- Symptomatic overdose (serious or nonserious) with IMP/NIMP.

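### Two rows of the AESI search table (SAP 15.6, Table 15-3) do not match the AESIs they should identify: the helminth search looks too narrow and the systemic hypersensitivity search has no step that selects systemic events

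*SAP*

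**What the plan says.** Protocol section 3, Table 1 makes "Incidence of adverse events of special interest (AESI") a secondary safety endpoint, and SAP Table 2-1 repeats it. Protocol 8.3 lists the AESIs. Two of them are "Helminthic infections", with no restriction on type, and "Systemic hypersensitivity reactions", restricted to systemic events. SAP 9.1.7 gives the same list and refers to Appendix 15.6 for the definitions, so Table 15-3 decides which reported terms enter the AESI outputs.

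In Table 15-3:

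- The helminth row opens with a plural abbreviation (printed HTLs, presumably HLTs) and then names one group, "Helminthic infections NEC".
- The systemic hypersensitivity row reads "SMQ: Hypersensitivity [Narrow"] and nothing more.
- The eosinophilia row starts from a group or term search, which is "followed by blinded medical review for selection of relative events".
- The severe conjunctivitis list includes the preferred term Seasonal allergy.

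Protocol 2.3 includes enterobiasis among the identified adverse drug reactions: "eosinophilia, enterobiasis and anaphylactic reaction, angioedema, serum sickness and arthralgia". The same section names systemic hypersensitivity as an important identified risk.

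**The concern.** A search table should return the events that its definition describes. Here one row appears to return fewer and another to return more.

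By its name, an NEC (not elsewhere classified) group holds what has no group of its own. If enterobiasis is coded elsewhere in the MedDRA version used, a literal reading of the helminth row leaves out of the AESI search the one worm infection that the protocol already attributes to the drug.

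In the hypersensitivity row, the word that defines the AESI, systemic, has no counterpart in the search. If the narrow SMQ contains non-systemic terms, those events count as AESIs.

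At stake is the accuracy of a stated secondary safety endpoint in a small trial. For a rare event, one case can decide whether the AESI table shows none or some.

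**Working it through.** The documents give no figure to reproduce, so the check is a comparison of definition with search, followed by a simple scale.

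**1. Helminth row.** Definition (protocol 8.3, SAP 9.1.7): all helminthic infections. Search (Table 15-3): one group, residual by name. The plural lead-in suggests that more than one group was intended. The abbreviation printed is not in the SAP's abbreviation list, which has HLT. As written, a programmer cannot tell whether other groups belong. The documents do not show where enterobiasis is coded: SAP 9.1 refers only to the MedDRA version in effect at database lock. Under-counting is therefore conditional on that coding.

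**2. Hypersensitivity row.** Definition: systemic reactions. Search: the narrow SMQ with no further condition. Other rows with a qualified or complex definition do carry a selection step:

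| AESI | Qualifier in the definition | Step in Table 15-3 that applies it |
|---|---|---|
| Eosinophilia | clinically symptomatic | blinded medical review |
| Conjunctivitis, blepharitis | severe | intensity recorded as severe in the e-CRF |
| Anaphylactic reactions | none | narrow SMQ plus a rule on pairs of terms close in time |
| Hypersensitivity | systemic | none |

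The SMQ's contents are not in the documents, so over-counting is also conditional.

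**3. Investigator-reported AESIs.** Protocol 8.3 has investigators report AESIs to the sponsor through e-CRF screens. Table 15-3 uses e-CRF check boxes for pregnancy and overdose only. The SAP does not say how an AESI reported by an investigator is reconciled with the dictionary search for the other rows.

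**4. Where an error would show.** SAP 9.1.7 plans tables of treatment-emergent AESIs, and of serious ones, by SOC, HLGT, HLT and PT. SAP 9.1 adds overview rows for participants with any AESI and any serious AESI, and a listing. No line by AESI category is planned. SAP 9.1.1 tabulates every treatment-emergent event by the same hierarchy and again by PT.

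**5. Scale.** Inputs: about 97 randomised, 2:1 (SAP 3.1).

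- Dupilumab: 97 × 2/3 = 64.7, about 65. One participant = 1/65 = 1.5%.
- Placebo: 97 × 1/3 = 32.3, about 32. One participant = 1/32 = 3.1%.

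The safety set requires at least one injection, so the actual denominators may be slightly smaller. The number of misclassified participants cannot be derived from the documents.

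**The case against.** The strongest objection is that neither error is demonstrated. Both depend on dictionary contents that the documents do not reproduce, and a helminth row with a plural and one entry could be a typing slip or a list that lost lines: other entries in the same table run together in the available text. This stands, and it is why the point is put as a mismatch with conditional consequences.

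Second, nothing disappears from the report. An enterobiasis case would appear by name in the general tables, and because the AESI tables go down to preferred term, a reader can see which terms make up the count. This also stands and limits the importance of the point.

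Third, few helminth cases are expected, because exclusion criterion E 18 removes participants with suspected or high-risk infection unless active infection is ruled out. A sensitive hypersensitivity search is also a defensible, cautious choice. Both are fair. But a sensitive search does not by itself yield an AESI limited to systemic reactions, and the SAP's own eosinophilia row shows how to move from one to the other.

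A reader might infer three stronger things that the documents do not support:

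- That investigator-reported AESIs are discarded. The SAP is silent on this, and silence is not a rule.
- That injection site reactions inflate the hypersensitivity count. Nothing shows that they are in the SMQ.
- That a particular percentage of participants would be wrongly shown with systemic hypersensitivity. The documents give no rate for non-systemic allergic events, and no such category line is planned.

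**Conclusion.** The mismatch between definition and search is on the face of the SAP and should be corrected. Followed literally, Table 15-3 may under-count helminth AESIs, if enterobiasis or another helminth infection is coded outside the NEC group, and may over-count hypersensitivity AESIs, if the narrow SMQ includes non-systemic terms. Both conditions are assumptions to be checked in the MedDRA version used, and the size of any net error is unknown.

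Each affected participant shifts an arm's AESI incidence by the amounts shown above, in the AESI tables and the overview rows only. The endpoint is descriptive, and no hypothesis test, alpha allocation or primary result depends on it. The Seasonal allergy entry is a minor further point: it is not a conjunctivitis term, but it counts in that row only when recorded as severe.

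**What to change.** Amend Table 15-3 before database lock and unblinding. SAP section 1 allows revisions up to lock.

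1. **Helminth row:** define the search as all helminth groups in the MedDRA version used, or their parent group term. Confirm that enterobiasis is captured. State that events the investigator reported as this AESI are included. If the dictionary check shows that enterobiasis is already captured, what remains of the search definition is mainly a correction of wording.
2. **Systemic hypersensitivity row:** keep the narrow SMQ as the first sift, then add the blinded medical review already specified for eosinophilia, to retain systemic events.
3. **Minor:** remove Seasonal allergy from the severe conjunctivitis list, or send it through the same review.

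The cost is a few table cells, one dictionary check and one blinded listing review. No new data collection is needed.
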